### Rationale for Phase I Endpoint

One of the objectives of the Phase I dose-finding part of the study will be to determine RP2D of avelumab in pediatric cancer subjects 0 to  $< 18$  years of age. The RP2D will be chosen based on the overall safety profile, PK, and pharmacodynamics. Determination of the RP2D is commonly the primary objective of dose-finding studies in oncology, including pediatric studies (Doussau 2012). The endpoint corresponding to this objective will be DLTs to determine the RP2D.

#### 5.2.1 Inclusion of Special Populations

All subjects in this study belong to a special population, namely children. See Section 5.2 for the rationale to include this population.

### 5.3 Selection of Trial Population

Only individuals who fulfill all inclusion criteria without matching any exclusion criteria may be enrolled into the trial as subjects. Prior to performing any trial assessments not part of the subject's routine medical care, the Investigator will ensure that the subject's parent(s)/legal guardian(s) have provided written informed consent and the subject has provided written assent (when age appropriate and per local regulations), following the procedure described in Section 9.2.

#### 5.3.1 Inclusion Criteria

Subject eligibility should be reviewed and documented by the Investigator or delegate of the Investigator's study team before subjects are included in the study.

For inclusion in the trial, all of the following inclusion criteria must be fulfilled:

1. Signed written informed consent form (ICF) before any trial-related procedure is undertaken that is not part of the standard patient management. The signed ICF indicates that the minor subject's parent(s)/legal guardian(s) have been informed of all pertinent aspects of the study, based on local regulations. Subjects also must provide assent when age appropriate and per local regulations.
2. Male and female subjects 0 to < 18 years of age at the time of first treatment dose.
3. Availability of formalin-fixed paraffin-embedded (FFPE) block containing tumor tissue or a minimum of 10 (preferably 25) unstained tumor slides (cut within 1 week) suitable for PD-L1 expression assessment, from a recently obtained (within 6 months) biopsy from a non-irradiated area. If tissue is unavailable in block or slides, a mandatory tumor biopsy must be performed prior to avelumab treatment for subjects in Phase II.
4. Subjects with histologically or cytologically proven diagnosis of malignant solid tumor (including CNS tumors) or lymphoma in Phase I, or specified tumor types in Phase II with measurable disease at Baseline (at least 1 unidimensional, radiographically measurable lesion based on RECIST v1.1).
5. Confirmed progression on or refractory to standard therapy, or no standard therapy available.
6. Lansky performance status  $\geq 50\%$  for subjects  $\leq 16$  years of age, or Karnofsky scale  $\geq 50\%$  for subjects  $> 16$  years of age.
7. Adequate bone marrow function, including:
  - a. Absolute neutrophil count  $\geq 1,000/\text{mm}^3$  or  $\geq 1 \times 10^9/\text{L}$  at least 5 days following the last dose of granulocyte colony stimulating factor
  - b. Platelets  $\geq 50,000/\text{mm}^3$  or  $\geq 50 \times 10^9/\text{L}$
  - c. Hemoglobin  $\geq 8$  g/dL (may have been transfused).
8. Adequate hepatic function, defined by:
  - a. a total serum bilirubin level  $\leq 1.5 \times$  the upper limit of normal range (ULN)
  - b. an aspartate aminotransferase (AST) level  $\leq 3.0 \times$  ULN
  - c. an alanine aminotransferase (ALT) level  $\leq 3.0 \times$  ULN or, for subjects with documented metastatic disease to the liver, AST and ALT levels  $\leq 5 \times$  ULN.

Patients with documented Gilbert disease are allowed if total bilirubin is  $< 3 \times$  ULN.
9. Adequate renal function, defined by an estimated creatinine clearance  $\geq 50$  mL/min (Phase I) or  $\geq 30$  mL/min (Phase II) according to the Cockcroft-Gault formula or by 24-hour urine collection for creatinine clearance or according to local institutional standard method.

10. Negative serum pregnancy test at Screening for all postmenarchal girls, girls  $\geq 10$  years of age, or per local or institutional guidelines.
11. Highly effective contraception (ie, methods with a failure rate of less than 1% per year) for both male and female subjects if the risk of conception exists. In this trial, a subject is considered to be of childbearing potential if, in the opinion of the Investigator, he/she is biologically capable of having children and is sexually active. (Note: The effects of the trial treatment on the developing human fetus are unknown; thus, women of childbearing potential and men must agree to use highly effective contraception, defined in [Appendix I](#) or as stipulated in national or local guidelines. Highly effective contraception must be used for the duration of trial treatment, and at least for 60 days after stopping trial treatment. Should a woman become pregnant or suspect she is pregnant while she or her partner is participating in this trial, the treating physician should be informed immediately).
12. Estimated life expectancy of at least 3 months.

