  - p. Serum chemistry: Full serum chemistry will be performed during Screening, CID1 (predose), EOT Visit, and the 30-day Safety Follow-up Visit. No need to repeat on CID1 if Screening assessments were performed within 7 days prior to that date. Core serum chemistries will be performed during other treatment visits. Core serum chemistry results must be available and reviewed prior to dose administration.
  - q. Urinalysis: A full urinalysis (dipstick plus microscopic evaluation) is required at Screening and at the EOT Visit, and a basic urinalysis (dipstick only) at each visit indicated prior to administration of trial drug. If the basic urinalysis is abnormal, then a full urinalysis should be performed.
  - r. Serum/urine pregnancy test: For female subjects of childbearing potential, measure serum  $\beta$ hCG at Screening and urine or serum  $\beta$ hCG thereafter. Results of the most recent pregnancy test should be available prior to the administration of avelumab.
  - s. T4 and TSH: Perform tests at Screening; CID1 (predose, if > 14 days after initial Screening); every 6 weeks for 2 subsequent measurements (eg, Week 6/7, Week 12/13); every 8 weeks thereafter (beyond Week 12/13); EOT Visit; and if clinically indicated. There is no need to repeat on CID1 if Screening assessments were performed within 14 days prior to CID1.
  - t. Cytokines: Refer to the Laboratory Manual for the specific cytokines to be measured.
  - u. Vaccination-related antibodies: Antibody titers for diphtheria, tetanus, and pneumococcal conjugate (PCV-7) will be measured.
  - v. HBV and HCV screening: The HBV screening panel includes 3 tests: hepatitis B surface antigen (HBsAg), hepatitis B surface antibody (HBsAb), and hepatitis B core antigen (HBcAb). The HCV screening test assesses the presence or absence of antibodies to HCV.
- CCI**
- x. Baseline tumor evaluation/staging: Tumor assessments will include all known or suspected disease sites. Imaging may include neck, abdomen, pelvis, and chest CT or MRI scans (if MRI is used, CT of chest is mandatory; for trial sites in Germany, only MRI is to be used). Baseline CNS imaging will not be required with the exception of symptomatic subjects to evaluate for CNS metastases. A bone scan (bone scintigraphy) or  $^{18}$ F-DG-PET/CT is required at Baseline in subjects with tumors known to metastasize to bone.

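### A postmenarchal girl judged not sexually active is tested for pregnancy at entry but has no scheduled test once she is on avelumab

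*Protocol*

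**What the plan says.** **Entry.** Protocol 5.3.1, criterion 10, asks for a "Negative serum pregnancy test at Screening for all postmenarchal girls". It extends to girls aged 10 years or over and closes with a local-practice branch: "years of age, or per local or institutional guidelines". None of these branches mentions sexual activity.

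**Later tests.** The pregnancy-test row of Table 1 has Screening, Cycles 1, 3, 5 and 7, every 4 weeks thereafter, End of Treatment and the 30-day visit. Footnote r decides who is tested. It begins "For female subjects of childbearing potential, measure serum" and provides for urine or serum tests after that. Section 7.1.3.1 (End of Treatment) and Section 7.4.4 (on-study tests) carry the same restriction, and Section 7.1.1 applies it to the Screening test.

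**The term.** Criterion 11 treats a subject as of childbearing potential if, in the Investigator's opinion, "he/she is biologically capable of having children and is sexually active". Section 7.1.1 and Appendix I repeat this definition.

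**The risk.** Criterion 11 states: "The effects of the trial treatment on the developing human fetus are unknown". Section 7.4.2 requires avelumab to stop at once if a subject becomes pregnant.

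**The concern.** The term was written for contraception, where sexual activity is a sensible condition, and was then reused to decide who is tested. Criterion 10 does not make a girl's test depend on what she or her family says about sexual activity. From Cycle 1 onward the protocol does, and it gives no reason for the change.

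What is at stake is fetal exposure in a minor. The rule to discontinue on pregnancy protects only if pregnancy is detected, and for this girl no detection step is scheduled. This is a subject-safety matter. Dose-limiting toxicity evaluation, endpoints and analyses do not depend on it.

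**Working it through.** **Step 1. Is she in the tested group?**

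| Provision | Who is tested | Is sexual activity a condition? |
|---|---|---|
| Criterion 10, Screening | All postmenarchal girls, girls aged 10 or over, or per local guidelines | No |
| Footnote r, Screening and on study | Childbearing potential | Yes, by definition |
| 7.1.1, Screening | Childbearing potential | Yes |
| 7.4.4, Screening and on study | Childbearing potential | Yes |
| 7.1.3.1, End of Treatment | Childbearing potential | Yes |

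At Screening the sections conflict, but criterion 10 governs: Section 5.3 enrolls only those who meet every inclusion criterion, and Section 5.4 has the criteria checked at the Screening Visit. After Screening no broader provision exists, so she drops out of the schedule.

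**Step 2. Does anything bring her back in?** Childbearing potential is collected with the demographic data at Screening (7.2.1), and Table 1 marks demographics at Screening only. The visit-by-visit query in 7.4.1.2 concerns changes in condition and may be answered by the representative. SAP 15.4.2 only lists pregnancy results. The Investigator may reclassify her at any time, but no visit or question is assigned to that.

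**Step 3. How many tests are not scheduled?** The dose day of cycle n is 1 + 14(n − 1). On-treatment tests fall at odd-numbered cycles. End of Treatment and the 30-day visit add 2 tests, both after the last dose.

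| Treated to | Cycles | Last dose | On-treatment tests (week) | Could change dosing | Total with the 2 later tests |
|---|---|---|---|---|---|
| 8 weeks | 4 | 1 + 14×3 = Day 43 | 1, 5 | 2 | 4 |
| 12 weeks | 6 | 1 + 14×5 = Day 71 | 1, 5, 9 | 3 | 5 |
| 24 weeks | 12 | 1 + 14×11 = Day 155 | 1, 5, 9, 13, 17, 21 | 6 | 8 |

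The 12-week case is close to the survival expected at entry (criterion 12: "Estimated life expectancy of at least 3 months").

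**Step 4. How old is her latest result at the last dose?** Age = (dose day − 1) + days from the Screening test to Day 1. I take that last term as 1 to 28 days, the upper end being the Screening window in 7.1.1.

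- 8 weeks: 42 + 1 = 43 to 42 + 28 = 70 days
- 12 weeks: 70 + 1 = 71 to 70 + 28 = 98 days
- 24 weeks: 154 + 1 = 155 to 154 + 28 = 182 days

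A girl on the schedule was last tested one cycle before each of these doses (Days 29, 57 and 141), so her result is 14 days old. These figures ignore visit windows and assume no omitted dose and no reclassification. The upper ends are worst cases.

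**The case against.** **The definition can be read differently.** Appendix I lists sexual abstinence among the contraceptive methods for subjects of childbearing potential. That sits awkwardly with a group defined as sexually active, and a site could conclude that abstinent girls belong in it and test them. This ambiguity stands. However, Appendix I evaluates abstinence as a contraceptive method and orders no test, and the definition given three times does not include her.

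**It may be deliberate.** Broad testing once at entry and risk-based testing afterwards can coexist. That is possible, but risk-based testing needs a step that updates the risk, and none is scheduled.

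**Other safeguards exist.** A reader might infer that an on-treatment pregnancy could be found only if the girl discloses sexual activity. The documents do not support that. Criterion 11 wants the treating physician told at once of a known or suspected pregnancy, and the two-weekly visits include weight and an examination directed to signs and symptoms. These routes are weaker than a scheduled test, but they are real.

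**Footnote r's dosing sentence.** The footnote also says "Results of the most recent pregnancy test should be available prior to the administration of avelumab". A reader might infer that dosing this girl on an old Screening result breaches it. But the same footnote leaves her outside its population, so the sentence does not clearly apply to her.

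**The totals flatter the point.** Of the 4, 5 and 8 tests, 2 in each case come after the last dose and cannot prevent dosing. One of the remainder is at Cycle 1, at most 28 days after the Screening test. This objection is right, so the relevant counts are 2, 3 and 6.

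**Conclusion.** The gap holds on the text. A postmenarchal girl judged not sexually active has no scheduled pregnancy test after Screening, although criterion 10 tests her at entry regardless of sexual activity. On-treatment detection then relies on the Investigator reclassifying her, on a reported or suspected pregnancy, or on examination findings. The missing tests that could change dosing are 2, 3 and 6 for treatment to 8, 12 and 24 weeks, if she is not reclassified and no dose is omitted.

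The documents give neither the number of such girls nor their pregnancy risk. SAP version 2.0 records that monotherapy evaluation ended after Phase I, so those affected are a subset of the 12 to 36 planned Phase I subjects of both sexes, aged 0 to under 18 years; the number may be small.

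A reader might infer from Sections 7.1.1 and 7.4.4 that a girl could enter untested. She could not, because criterion 10 has to be met. At Screening this is a drafting conflict only. Overall this is a low-cost subject-safety improvement and does not bear on the validity of the results.

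**What to change.** - **Screening:** in footnote r and Sections 7.1.1 and 7.4.4, replace childbearing potential with the criterion 10 population.
- **After Screening:** in footnote r and Sections 7.1.3.1 and 7.4.4, schedule the existing urine or serum tests for all postmenarchal girls, including those who reach menarche on study, whatever their reported sexual activity.
- **Premenarchal girls:** no repeat test, but a brief menarche question at the four-weekly visits.
- **Contraception:** keep the sexual-activity condition here only (criterion 11, the contraception text of 7.1.1, and Appendix I).

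**Cost.** The change rewords one footnote and three sections. It adds about 4 to 8 urine tests per affected girl treated for 8 to 24 weeks, including the two after the last dose. No visit is added: the urinalysis row of Table 1 has the same visits as the pregnancy row, and footnote q already asks for "a basic urinalysis (dipstick only) at each visit indicated prior to administration of trial drug". Sites must ask the menarche question and handle a minor's result under local confidentiality rules. Endpoints and analyses do not change.

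A scheduled reassessment of sexual activity would be less intrusive, but it would still rest on what a minor or her representative is willing to report.

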### 5.3.2 Exclusion Criteria

Subjects are not eligible for this trial if they fulfill any of the following exclusion criteria:

1. Prior therapy with any antibody or drug targeting T-cell coregulatory proteins (immune checkpoints), such as PD-1, PD-L1, or cytotoxic T-lymphocyte antigen-4.
2. Concurrent anticancer treatment (eg, cytoreductive therapy, radiotherapy, immune therapy, cytokine therapy, monoclonal antibody, targeted small molecule therapy) or any investigational drug **within 2 weeks** prior to start of study treatment, or not recovered from AEs related to such therapies, with the following exceptions:
  - a. Short-course, bone-directed, palliative radiotherapy delivered in a normal organ-sparing technique is permitted (concurrently or within the pretreatment period).
  - b. Erythropoietin and darbepoetin- $\alpha$  are permitted.
  - c. Hormonal therapies acting on the hypothalamic-pituitary-gonadal axis are permitted (ie, luteinizing hormone-releasing hormone agonists/antagonists). No other hormonal anticancer therapy is permitted.
3. Major surgery for any reason, except diagnostic biopsy, within 4 weeks prior to start of study treatment and/or if the subject has not fully recovered from surgery within 4 weeks of the trial treatment.
4. Subjects receiving immunosuppressive agents (such as steroids) for any reason should be tapered off these drugs before initiation of the trial treatment, with the following exceptions:
  - a. Subjects with adrenal insufficiency may continue corticosteroids at physiologic replacement dose.

- b. Administration of steroids through a route known to result in a minimal systemic exposure (topical, intranasal, intra-ocular, or inhalation) is permitted.
  - c. Previous or ongoing administration of systemic steroids for the management of an acute allergic phenomenon is acceptable as long as it is anticipated that the administration of steroids will be completed in 14 days, or that the dose after 14 days will be equivalent to the physiologic replacement dose.
5. Previous malignant disease (other than the tumor disease for this trial) within the last 5 years (except adequately treated non-melanoma skin cancers, carcinoma in situ of skin, bladder, cervix, colon/rectum, breast, or prostate) unless a complete remission without further recurrence was achieved at least 2 years prior to study entry and the subject was deemed to have been cured with no additional therapy required or anticipated to be required
6. Prior organ transplantation, including allogeneic stem cell transplantation.
7. Significant acute or chronic infections, including, among others:
  - a. Known history of human immunodeficiency virus (HIV) or known acquired immunodeficiency syndrome.
  - b. Hepatitis B virus or hepatitis C virus (HCV) infection (defined as HBV surface antigen positive and HBV core antibody positive with reflex to positive HBV DNA or HBV core antibody positive alone with reflex to positive HBV DNA; or positive HCV antibody with reflex to positive HCV RNA).
  - c. Active tuberculosis (history of exposure or history of positive tuberculin test; plus presence of clinical symptoms, physical or radiographic findings). Subjects with latent tuberculosis infection who are deemed to require treatment by the Investigator are not eligible.
8. Active autoimmune disease that might deteriorate when receiving an immunostimulatory agent:
  - a. Subjects with diabetes type 1, vitiligo, psoriasis, or hypothyroid/hyperthyroid disease not requiring immunosuppressive treatment are eligible.
  - b. Administration of steroids through a route known to result in a minimal systemic exposure (topical, intranasal, intra-ocular, or inhalation) is acceptable.
9. Known prior severe hypersensitivity to investigational product or any component in its formulations.
10. Persisting toxicity related to prior therapy of Grade > 2 NCI-CTCAE v4.03 (except neuropathy [see exclusion criterion #11] and alopecia).
11. Neuropathy  $\geq$  Grade 3
12. Pregnancy or lactation

13. Known alcohol or drug abuse as determined by the Investigator
14. History of uncontrolled intercurrent illness, including but not limited to:
  - a. Hypertension uncontrolled by standard therapies (not stabilized to 150/90 mmHg or lower)
  - b. Uncontrolled active infection.
  - c. Uncontrolled diabetes (eg, hemoglobin A1c  $\geq$  8%).
15. Clinically significant (ie, active) cardiovascular disease: cerebral vascular accident/stroke or myocardial infarction (< 6 months prior to enrollment), unstable angina pectoris, congestive heart failure (New York Heart Association Classification Class  $\geq$  II), clinically significant ventricular arrhythmia (ie, ventricular tachycardia, ventricular fibrillation, or Torsades de pointes), diagnosed or suspected congenital or acquired prolonged QTc syndrome, or serious uncontrolled cardiac arrhythmia requiring medication/active intervention.
16. All other significant diseases (eg, severe gastrointestinal conditions such as diarrhea, colitis, inflammatory bowel disease, ulcer, or pneumonitis; end-stage kidney disease or chronic kidney disease requiring hemodialysis; or uncontrolled asthma), which, in the opinion of the Investigator, might impair the subject's tolerance of trial treatment.
17. Any psychiatric condition, including recent (within 10 days) or active suicidal ideation or behavior that would prohibit the understanding or rendering of informed consent or that would limit compliance with trial requirements.
18. Administration of a live vaccine within 28 days prior to study entry and while on trial.
19. Rapidly progressive disease.
20. Known congenital immunodeficiency.

#### **5.4 Criteria for Initiation of Trial Treatment**

The inclusion and exclusion criteria will be checked at the Screening Visit. Individuals who do not meet the criteria for initiating treatment (screen failures) may be rescreened. The parent(s)/legal guardians of rescreened participants will sign a new ICF, a new subject number will be assigned, and the Screening procedures will be conducted.

#### **5.5 Criteria for Subject Withdrawal**

Subjects who have experienced a complete response (CR) should be treated for a minimum of 12 months based on clinical judgment of benefit and/or until confirmed progression per irRECIST, unacceptable toxicity, or any criterion for withdrawal occurs, after confirmation of response as specified in this protocol. Each subject will be followed for additional 12 months after end of treatment.

### 5.5.1 Withdrawal from Trial Therapy

A subject must be withdrawn from avelumab if any of the following occurs:

- Subject or his/her parent(s)/legal representative(s) withdraw consent.
- Subject lost to follow up.
- Participation in another clinical trial.
- Any events that unacceptably endanger the safety of the subject.
- Subjects meeting the definition of confirmed PD while on treatment based on irRECIST. Subjects who experience confirmed disease progression may be permitted to continue treatment with avelumab per Section 6.2.1.
- Significant clinical deterioration (clinical progression), defined as new symptoms that are deemed by the Investigator to be clinically significant or significant worsening of existing symptoms.
- Unacceptable toxicity.
- Occurrence of an exclusion criterion that is clinically relevant and affects the subject's safety, if trial treatment discontinuation is considered necessary by the Investigator and/or Sponsor.
- Therapeutic failure requiring urgent additional drug (if applicable).
- Occurrence of any Grade  $\geq 3$  ADRs or as defined in Section 5.1.3.2.
- Occurrence of AEs resulting in the discontinuation of the trial treatment being desired or considered necessary by the Investigator and/or the subject.
- Occurrence of pregnancy.
- Use of a prohibited concomitant drug, as defined in Section 6.5.2, where the predefined consequence is withdrawal from the trial treatment if considered necessary by the investigator or the Sponsor.
- Noncompliance (see Section 6.9).

